The Follow-up period starts after the end-of-treatment and lasts until the end-of-study.

The End of Study (EOS) is Day 60 (± 3) or date of early study termination unless ongoing SAEs, if applicable.

The End of Trial (EOT) will be when the Last Patient Last Visit (LPLV) has occurred.

All patients will receive the best available care as per applicable local, institutional, national, supranational COVID-19 treatment guidelines.

Patients assigned to the experimental arms will receive, in addition, plitidepsin as a 1-h IV infusion, during Days 1 to 3.

Patients randomised to the control arm may receive a regulatory-approved antiviral treatment in addition to the BSC.

For prevention of infusion-related (i.e., plitidepsin-related) reactions (IRRs), allergic reactions and emesis reactions, administration of premedications is mandatory in the experimental arms.

All consenting patients discontinuing early from the study before the EOS visit should complete the early termination/withdrawal procedures.

Duration of Study Periods:

- Screening period: From the day of ICF signing prior to randomisation).
- Day 1: Date of randomisation. Treatment must be started on the same date.
- Treatment period: from Day 1 to 24 h after the last dose of the antiviral therapy; if no antiviral was given in the control arm, then the treatment period will finish on Day 4, for data management purposes.
- Follow-up period: From the end-of-treatment to end-of-study.
- EOS: Day 60 (± 3) or date of early study termination unless ongoing SAEs, if applicable.
- Overall study duration: 60 (± 3) days since randomisation.
- End of the trial will be when the Last Patient Last Visit (LPLV) has occurred.

Independent Data Monitoring Committee (IDMC):

An IDMC was established to provide study oversight. The IDMC was composed of individuals external not only to the Sponsor but also to the trial managers (including Sponsor's and Contract Research Organisation's [CRO] medical monitors) and study investigators.

Given the decision to terminate the study due to low accrual, the IDMC activity has been discontinued and there will not be distinction between blinded and unblinded procedures.

Study “Stopping rules”

The Sponsor may suspend or terminate the study if:

- New toxicological or pharmacological findings or safety issues that invalidate the earlier positive benefit-risk assessment occur;
- Significant safety concerns, according to the Sponsor’s criteria, arise during the conduct of the study;

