8.3 Endpoints

Efficacy primary endpoint:

- 1-month† all-cause mortality rate. †(Day 30 since randomisation).

Key secondary endpoint:

- Time to confirmed negativisation in SARS-CoV-2 antigen test or RT-PCR Ct > 30.

Secondary endpoints:

Efficacy secondary endpoints

- Time to sustained end of COVID-related hospital care from the time of randomisation. Sustained discharge is defined as no subsequent admission within 30 days of initial end of hospital care [up to day 60 (± 3)], related to either COVID-19 or COVID-19 therapy.
- Time to sustained improvement (defined in Protocol Section 7.1.3) and resolution of selected COVID signs/symptoms (See Protocol Appendix 10 - COVID-19 signs/symptoms checklist).
- Distribution of patients according to their clinical status by the 11-category WHO Clinical Progression Scale, at Days 4 (± 1), 8 (± 1), 15 (± 1), 30 (± 2), and 60 (± 3) (See Protocol Appendix 1 – 11-Point World Health Organization (WHO) Clinical Progression Scale).
- Percentage of patients requiring oxygen therapy on Days 4 (± 1), 8 (± 1), 15 (± 1), 30 (± 2), and 60 (± 3).
- Time to sustained discontinuation (i.e., at least 7 days) of oxygen supplementation.

Safety secondary endpoints

Frequency of the following events (all-cause and drug-related):

- Treatment-emergent adverse events (TEAEs);
- TEAEs \geq grade 3 according to the National Cancer Institute [NCI]-Common Terminology Criteria for AEs (CTCAE v.5.0);
- Adverse events of special interest (AESIs);
- Serious adverse events (SAEs);
- Drug related Serious Adverse Events (i.e., SARs);
- Adverse events leading to treatment discontinuation; and
- Deaths (COVID-19-related/all).
- Change respect to baseline* in individual study-defined laboratory parameters (See Protocol Section 5.7, 5.8 and 5.9 and Protocol Appendix 8 – Clinical Laboratory Analyses).
- Change respect to baseline* in individual vital signs (See Protocol Section 5.7, 5.8 and 5.9).

*Baseline = latest test performed between screening and drug administration

Other Secondary/Exploratory Endpoints

- Percentage of patients requiring advanced oxygen support on Days 4 (± 1), 8 (± 1), 15 (± 1), 30 (± 2) and 60 (± 3).
- Time to intensification of respiratory support (WHO >5) (See Protocol Appendix 1 – 11-Point World Health Organization (WHO) Clinical Progression Scale).
- Total duration of advanced oxygen support.
- Percentage of patients requiring high-flow oxygen on Days 4 (± 1), 8 (± 1), 15 (± 1), 30 (± 2), and 60 (± 3).

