8.6.2.1 Full Analysis Set (FAS) Population

All randomised patients who have taken at least 1 dose of study treatment (plitidepsin or control) and have completed follow-up for survival until day 30 (± 2). Patients who die before the end of follow-up period will also be included in the FAS population. FAS population will be analysed according to their randomised treatment arm.

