9.0 Conventions and Derivations

Variables reported with different units will be homogenized to standardized variables following the International System of Units (e.g. laboratory tests, biometrical assessments...) unless otherwise specified.

By default, all results will be rounded to one decimal place, except when variables are integer, which will be reported without decimals (e.g., age in years). Percentages for 0 counts will not be presented and 100% values will be presented with no decimal places. For representing p-values four decimals will be selected as default but they could be rounded to fewer decimals if necessary.

Missing values will not be included in the calculation of outputs. Unless otherwise noted, missing data will not be imputed or carried forward.

For patients who discontinue treatment due to adverse events (related or not to study treatment) every effort should be made to remain under study follow-up, anyway, if information is lost before day 28 the conservative value of death will be also imputed.

Patients with no available data for any time-to event efficacy endpoint will be censored at time 0. EOS: Day 60 (± 3) or date of early study termination, if applicable. Patients not yet achieving the time to event endpoint will be censored at the last valid assessment prior to EOS. Efron's method will be used to handle ties.

Assessment windows as specified in the clinical protocol will be respected, see protocol Appendix 13 'Schedule of Assessments and Procedures' for definitions of trial days. Baseline is defined as latest test performed between screening and drug administration.

Change from baseline (%) is defined as: $(\text{test value} - \text{baseline value}) / \text{baseline value} \times 100$.

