11.8 Summary of Statistical Tests

All the main characteristics for estimands to fulfill study objectives will be defined as footnotes in each table following a similar structure than primary estimand definition. Below it can be found the endpoints to measure the variable definition and the analysis method to be used. Treatment attribute is maintained as 'participants will be randomised to receive plitidepsin versus control in each group' whereas applicable and sensitivity analyses according populations defined in 8.5 will be calculated. For intercurrent events, while applicable, a treatment-policy strategy as defined for the primary estimand will be followed.

Table 3 Summary of statistical tests

Endpoints	Analyses	Population
Efficacy primary endpoint		
1-month all-cause mortality rate.	-Frequencies	-FAS population
Key secondary endpoint		
Time to confirmed negativisation in SARS-CoV-2 antigen test or RT-PCR Ct > 30.	-Kaplan-Meier (unstratified)	-FAS population

Endpoints	Analyses	Population
Efficacy secondary endpoints		
Time to sustained end of COVID-related hospital care from the time of randomisation. Sustained discharge is defined as no subsequent admission within 30 days of initial end of hospital care [up to day 60 (± 3)], related to either COVID-19 or COVID-19 therapy	-Kaplan-Meier (unstratified)	-FAS population
Time to sustained improvement (defined in Protocol Section 7.1.3) and resolution of selected COVID signs/symptoms (See Protocol Appendix 10 - COVID-19 signs/symptoms checklist).	-Kaplan-Meier (unstratified)	-FAS population
Distribution of patients according to their clinical status by the 11-category WHO Clinical Progression Scale, at Days 4 (± 1), 8 (± 1), 15 (± 1), 30 (± 2), and 60 (± 3) (See Protocol Appendix 1 – 11-Point World Health Organization (WHO) Clinical Progression Scale).	-Frequencies	-FAS population
Percentage of patients requiring oxygen therapy on Days 4 (± 1), 8 (± 1), 15 (± 1), 30 (± 2), and 60 (± 3).	-Frequencies	-FAS population
Time to sustained discontinuation (i.e., at least 7 days) of oxygen supplementation.	-Kaplan-Meier (unstratified)	-FAS population
Safety secondary endpoints		
Treatment-emergent adverse events (TEAEs).	-Frequencies (severity grade by NCI-CTCAE v5)	-As treated population
TEAEs \geq grade 3 according to the National Cancer Institute	-Frequencies	-As treated population

Endpoints	Analyses	Population
[NCI]-Common Terminology Criteria for AEs (CTCAE v.5.0).		

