Percentage of patients receiving immune-modulating drugs on Days 1, 4 (± 1), 8 (± 1), 15 (± 1), 30 (± 2), and 60 (± 3).	-Frequencies	-FAS population
Time to onset of additional (i.e., not present at baseline) antiviral drugs.	-Kaplan-Meier (unstratified)	-FAS population

Endpoints	Analyses	Population
Percentage of patients receiving subsequent antiviral drugs (i.e., not present at baseline) on Days 4 (± 1), 8 (± 1), 15 (± 1), 30 (± 2), and 60 (± 3).	-Frequencies	-FAS population
Percentage of patients with a new infection by Days 4 (± 1), 8 (± 1), 15 (± 1), 30 (± 2), and 60 (± 3).	-Frequencies	-FAS population
Cumulative mortality (all-cause and related to COVID-19) by Days 4 (± 1), 8 (± 1), 15 (± 1), 30 (± 2), and 60 (± 3).	-Frequencies	-FAS population
Percentage of patients in each study group who require subsequent admission within 30 days of initial end of hospital care [up to day 60(± 3)], related to either COVID-19 or COVID-19 therapy.	-Frequencies	-FAS population
Change respect to Day 1 in the viral load of SARS-CoV-2, measured by RT-PCR, by Days 4 (± 1), 8 (± 1), 15 (± 1), 30 (± 2), and 60 (± 3), in each study group.	-Summary statistics	-FAS population
Percentage of patients in each study group with undetectable viral load, by Days 4 (± 1), 8 (± 1), 15 (± 1), 30 (± 2), and 60 (± 3).	-Frequencies	-FAS population
Time to either undetectable viral load of SARS-CoV-2 or > 2 logs reduction respect to Day 1.	-Kaplan-Meier (unstratified)	-FAS population
Change respect to baseline in inflammatory biomarkers (C-reactive protein [CRP], procalcitonin, lactate dehydrogenase [LDH], ferritin, neutrophil-to-lymphocyte ratio, and multiplex cytokines assay,	-Summary statistics	-FAS population

Endpoints	Analyses	Population
by Day 4 (± 1), 8 (± 1), 15 (± 1) and 30 (± 2) and 60 (± 3).		
Change respect to baseline in individual serological assessments against SARS-CoV-2, by Days 30 (± 2), and 60 (± 3).	-Summary statistics	-FAS population
Change respect to baseline in individual T-cell response against SARS-CoV-2 by Days 30 (± 2), and 60 (± 3).	-Summary statistics	-FAS population
Change respect to baseline to Days 15 (± 1), and 30 (± 2) in chest X-ray findings (Brixia score, centrally assessed) (Protocol Appendix 9 – Brixia Score).	-Summary statistics	-FAS population
Percentage of patients requiring modification of the therapy (drugs, dose or schedule) for the underlying disease.	-Frequencies	-FAS population

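### Readmission is tabulated over the whole FAS, where in-hospital deaths read as not readmitted, and the Day 60 cap sets a lower bar for later discharges

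*SAP*

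**What the plan says.** **Readmission.** SAP Section 11.8, Table 3, lists "Percentage of patients in each study group who require subsequent admission within 30 days of initial end of hospital care", capped at Day 60 (±3) and limited to admissions related to COVID-19 or its therapy. The analysis is frequencies and the population is the FAS. No separate denominator is stated.

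**The FAS.** SAP Section 8.6.2.1 requires that patients "have completed follow-up for survival until day 30" (±2), and adds: "Patients who die before the end of follow-up period will also be included in the FAS population". Follow-up beyond about Day 30 is not needed for membership.

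**Sustained discharge.** SAP Section 8.3 states: "Sustained discharge is defined as no subsequent admission within 30 days of initial end of hospital care", followed by the same Day 60 (±3) cap. Table 3 assigns this endpoint to unstratified Kaplan-Meier in the FAS.

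**End of study.** SAP Section 8.2 sets it at Day 60 (±3) "or date of early study termination unless ongoing SAEs, if applicable".

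**General rules.** SAP Section 9.0 says "Patients not yet achieving the time to event endpoint will be censored at the last valid assessment prior to EOS" and "Missing values will not be included in the calculation of outputs". On intercurrent events, Section 11.8 says: "For intercurrent events, while applicable, a treatment-policy strategy as defined for the primary estimand will be followed". Neither section says how to treat death before discharge, or a discharge observed for less than 30 days.

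**The concern.** Only a patient who has left hospital can be readmitted. If everyone in the FAS stays in the denominator, a death before discharge lowers the readmission percentage exactly as a good outcome would. A treatment that kept more patients alive to be discharged could then look worse on readmission when the risk after discharge was the same.

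The cap creates a second imbalance. A patient discharged on Day 10 must stay out of hospital for 30 days; one discharged on Day 50 need only do so for about 10. The slower arm is judged more leniently.

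In the time-to-discharge curve, censoring a patient at death treats that patient as someone who might still have been discharged later. This lifts the curve, and lifts it more in the arm with more deaths.

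No formal tests are planned, but SAP Section 6.0 intends the descriptive tables to let readers compare the arms numerically. The raw percentages and curves will carry that comparison.

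**Working it through.** The documents give no expected rate, event count or power for either endpoint, so there is no plan figure to reproduce. Mortality of 20% and 7.5% is the example in SAP Section 8.5. Readmission risks and lengths of stay below are assumptions.

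**1. Denominator.** Suppose all deaths occur in hospital before discharge and everyone else is discharged. Then

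FAS readmission % = (1 − in-hospital death rate) × readmission risk among those discharged.

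| Assumed risk, both arms | Control: 0.80 × risk | Plitidepsin: 0.925 × risk |
|---|---|---|
| 5% | 4.0% | 4.6% |
| 15% | 12.0% | 13.9% |
| 30% | 24.0% | 27.75% |

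The ratio is 0.80 / 0.925 = 0.865 throughout: a relative reduction of 13.5% in the arm with more deaths, with no true difference in readmission. At 15% the gap is 13.875 − 12.0 = 1.875 points, or 0.01875 × 20 = 0.375 of a patient at the planned 20 per arm.

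A whole-patient illustration: 20 per arm and 3 readmissions in each, with 19 discharged on plitidepsin and 15 on control (4 deaths, 1 still admitted). Over the FAS both arms show 3/20 = 15%. Among those discharged the figures are 3/19 = 15.8% and 3/15 = 20.0%.

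**2. Observation window.** Days observed after discharge = min(30, EOS day − discharge day). The last discharge day with a full 30 days is EOS − 30: Day 27, 30 or 33 for an EOS visit on Day 57, 60 or 63.

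With EOS on Day 60, a constant hazard and 30-day risk R, the chance of a readmission being seen is 1 − (1 − R)^(days/30).

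| Discharge day | Days observed | R = 10% | R = 15% | R = 20% |
|---|---|---|---|---|
| 30 or earlier | 30 | 10.0% | 15.0% | 20.0% |
| 40 | 20 | 6.8% | 10.3% | 13.8% |
| 45 | 15 | 5.1% | 7.8% | 10.6% |
| 50 | 10 | 3.5% | 5.3% | 7.2% |

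**3. Sustained discharge with deaths censored.** Take constant cause-specific hazards, with death and discharge the only ways out and readmission ignored. Let λ = ln 2 / median stay, and let s be the share of exits that are deaths. By Day 60:

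- 1 − KM with deaths censored = 1 − exp(−(1 − s) × λ × 60)
- cumulative incidence with death competing = (1 − s) × (1 − exp(−λ × 60))

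| Death share | Assumed median stay | 1 − KM | Cumulative incidence | Excess |
|---|---|---|---|---|
| 20% | 8 days | 0.984 | 0.796 | 0.188 |
| 20% | 15 days | 0.891 | 0.750 | 0.141 |
| 7.5% | 8 days | 0.992 | 0.920 | 0.072 |
| 7.5% | 15 days | 0.923 | 0.867 | 0.056 |

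The true gap between the arms, 0.920 − 0.796 = 0.124 at an 8-day median, shrinks to 0.992 − 0.984 = 0.008. At 15 days, 0.867 − 0.750 = 0.117 shrinks to 0.923 − 0.891 = 0.032.

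**The case against.** The best defence has five parts.

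- **The denominator is inferred.** Table 3 names a population, not a denominator. If never-discharged patients were coded as missing, the Section 9.0 rule would remove them, and Section 11.8 promises estimand footnotes. This is fair: the FAS reading is the literal one, not an explicit instruction. But nothing says such patients are coded missing, so two programmers could produce different percentages from the same data.
- **The cap is stated openly.** This stands. A reader might infer that the endpoints demand 30 days that late discharges cannot have; the bracketed limit shows they do not. What remains is unequal time at risk and no rule for short windows.
- **Deaths are not scored as discharges.** A reader might infer that an in-hospital death counts as success on both endpoints. Under Section 9.0 it is censored in the sustained-discharge analysis. The flaw there is how a competing event is handled.
- **Closure is not shown to have shortened follow-up.** The early-termination clause in the EOS definition also stands in Protocol Sections 3 and 5.1. No text says that enrolled patients lost their Day 60 visit.
- **The effect is small and visible.** Readmission is an other secondary/exploratory endpoint, cumulative mortality is tabulated in the same FAS, and no tests are run. The FAS proportion also respects randomisation, which a discharged-alive proportion does not. All of this stands. It argues for adding a figure beside the FAS one rather than replacing it, and for modest weight.

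**Conclusion.** The point holds as a matter of presentation and definition. Read literally, the readmission percentage favours the arm with more in-hospital deaths, by a factor of 0.865 at the plan's mortality rates if readmission risk is equal and all deaths precede discharge. Discharges after Day 27 to Day 33, depending on the EOS visit, satisfy the capped wording with less than 30 days of observation. Censoring in-hospital deaths raises the Day 60 discharge estimate by about 14 to 19 points at a 20% death share and 6 to 7 points at 7.5%, under the constant-hazard model and assumed stays of 8 to 15 days.

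The readmission risks, lengths of stay and share of late discharges are assumptions, and actual arm sizes will be below plan after closure for low recruitment. The primary endpoint is untouched. The documents do not support saying that deaths count as sustained discharges, or that the closure truncated these windows. This is an inexpensive improvement to descriptive tables.

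**What to change.** **Readmission.** Keep the FAS figure. Beside it, report readmission with patients discharged alive as the denominator. By arm, show the number discharged alive, in-hospital deaths, patients not yet discharged, and patients discharged with a complete 30-day window. State in the footnote how never-discharged patients are coded.

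**Sustained discharge.** Flag discharges with an incomplete window and show the result with them counted and with them censored. Keep in-hospital deaths in the risk set as never discharged, or use cumulative incidence with death as a competing event. Do not discard Day 31 to Day 60 discharges; in a trial this small that loses observed data and alters a protocol-defined endpoint.

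**Cost.** A few table rows and footnotes, which Section 11.8 already provides for. Protocol Section 7.1.4 already records the days of discharge, subsequent admission and death up to Day 60, so no new collection is needed. The discharged-alive figure describes a subset formed after randomisation, so it should be labelled descriptive and not read as a randomised comparison.

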11.10 Pooled and Subgroup Analyses

Exploratory pooled analyses will be performed for safety endpoints.

<NOTE: Due to the premature study closure no specific outputs will be generated for subgroup analysis>.

11.11 Pharmacokinetic and Pharmacodynamics Analyses

These analyses will be detailed and reported in separate documents.

13.0 Statistical Software

JAGS program running in R version 4.2.1 (3) on Microsoft Windows 10 for simulations and sample size derivation for randomised groups (1-3) and <https://www2.ccrb.cuhk.edu.hk/stat/phase2/Fleming.htm> for Non-controlled group 4.

SAS® v.9.4 or higher will be used for statistical analysis outputs.

14.0 Glossary of Abbreviations

AE	Adverse Event
AESI	Adverse Event of Special Interest
ALC	Absolute Lymphocyte Count
ATC	Anatomical Therapeutic Chemical
BSC	Best Standard Care
CBHM	Calibrated Bayesian Hierarchical Model
CKD-EPI	Chronic Kidney Disease Epidemiology Collaboration
COVID-19	Coronavirus disease 2019
CRO	Contract Research Organisation
CRP	C- reactive Protein
CRF	Case Report Form
eCRF	Electronic Case Report Form
ECMO	Extracorporeal Membrane Oxygenation
EOS	End of Study
FAS	Full Analysis Set
FPI	First Patient In
GCP	Good Clinical Practice
GGT	Gamma Glutamyl Transferase
h	Hour
ICF	Informed Consent Form
ICU	Intensive Care Unit
IDMC	Independent Data Monitoring Committee
IL-6	Interleukine-6
IMP	Investigational Medicinal Product
IRR	Infusion-related (i.e., plitidepsin-related) Reactions
IV	Intravenous
JAGS	Just Another Gibbs Sampler
LDH	Lactate Dehydrogenase
LPLV	Last Patient Last Visit
MCMC	Markov-chain Monte Carlo
MedDRA	Medical Dictionary for Regulatory Activities
NCI-CTCAE	National Cancer Institute Common Terminology Criteria for Adverse Events
NLR	Neutrophil-to-Lymphocyte Ratio
PK/PD	Pharmacokinetic(s)/Pharmacodynamic(s)
PP	Per Protocol
Q1-Q3	Interquartile Range
RBC	Red Blood Cells
RT-PCR	Real Time Polymerase Chain Reaction
SAE	Serious Adverse Event

Statistical Analysis Plan (SAP)
Version Date: 20Mar2024

Sponsor: PharmaMar

Protocol no: AV-APL-B-002-22

SAR	Drug related Serious Adverse Event
SARS-CoV-2	Severe Acute Respiratory Syndrome Coronavirus Type 2
STD	Standard Deviation
TEAE	Treatment Emergent Adverse Event
vs	versus
WHO	World Health Organization
